# 2.5. Outcomes and Timing of Assessments.

# Table 6. Outcomes

Study Variable	Instrument	Outcome (Range)
Maternal: Measured at Baselin	e and 3*-, 6- and 12-months post-randomization	
Maternal Characteristics**	Trial Baseline Questionnaire 53,54	Self-reported age, education level, marital status, immigrant status and ethnicity, clinical history with depression or anxiety (severity, chronicity, number of prior episodes, and age at first episode, occupational status, number of children, pregnancy intention, pregnancy history, delivery and birth, sexual orientation.
Depressive Symptoms	Edinburgh Postnatal Depression Scale (EPDS)41	Mean continuous score of a 10-item scale (0-30)
Anxiety Symptoms	Generalized Anxiety Disorder Scale (GAD-7)42	Mean continuous score of a 7-item scale (0-21)
Response & Remission	Patient Health Questionnaire-9 (PHQ-9) 	Response: PHQ<10 Remission is defined as PHQ<5
Perceived Support	Multidimensional Scale of Perceived Social Support 	Mean continuous score of a 12-item scale (1-84)
Disability Assessment	World Health Organization Disability Assessment Schedule (WHODAS) 	Mean continuous score of a 12-item scale (0 – 48)
Quality of Life Assessment	EQ5D-5 Level (EQ5D-5L) 	Mean continuous score of a 5-item scale (1-25)
Trauma Symptoms	Abbreviated PTSD Checklist (PCL-6) 	Mean continuous score of a 6-item scale (1-30)
Patient-Reported Activation	Premium Abbreviated Activation Scale 	Mean continuous score of a 5-item scale (0-20)
Patient Satisfaction***	Client Satisfaction Questionnaire-8 (CSQ-8)61	Mean continuous score of an 8-item scale (1-32)
Therapeutic Alliance***	Working Alliance Inventory-Short Revise (WAI-SR)62	Mean continuous score of a 12-item scale (1-60)
Health Service Utilization	Health Service Utilization Form 	3, 6 months - Total score of a 16-item scale (0-32); 12 months – Total score of a 19-item scale (0 – 38)
Treatment Preference**	Delivery of treatment and treatment provider preference	Score of 0 or 1
COVID-19 Exposure	1-item question on COVID-19 exposure	Self-reported
Health Benefits Access and Use	2-item question on access and use of health benefits	Self-reported Self-reported
Sexual Orientation o	2-item question on sexual orientation	Self-reported
Home Visit Survey □	4-item question on home visit perspective	Self-reported

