#### 2.6. Sample Size

The primary outcome measure will be participant's EPDS mean score at 3 months after randomization; the assessment period will be extended in the event that there is a hiatus to treatment due to significant perinatal-related life events (e.g., giving birth, obstetrical complications, COVID-19) or to one week after the last session if participants complete treatment after the 3 month-post randomization period. The study is designed to be a noninferiority trial with four arms: telemedicine specialist, telemedicine non-specialist, in-person specialist, in-person non-specialist. The two primary hypotheses are that telemedicine will be non-inferior to in-person, and that non-specialist delivery agents will be non-inferior to specialist delivery agents. The sample size calculation is based on an EPDS mean estimate of 7.93 (SD=4.68). Using a non-inferiority margin of 10% (i.e., EPDS score of 0.79) in relation to the mean), and an alpha=0.05 for our first comparison (NSP vs. SP) we require 431 participants in each of the two groups to provide greater than 80% power. To account for 10% drop out, the sample size is inflated to N=958 (479 per group, NSP vs. SP). Using a non-inferiority margin of 13% (i.e., EPDS score of 1.03 in relation to the mean), and an alpha=0.05 for our second comparison (TM vs. IP), we require an additional 268 IP participants. When combined with the 958 TM participants, this yields a total study sample size of N=1,226 which accounts for 10% loss to follow-up. Previous randomized non-inferiority trials have demonstrated that a 14% non-inferiority margin can be considered clinically meaningful.

We are planning a final sample size of N=1,230, four more participants than the power calculation requires. The reason for this n=4 over recruitment, is to provide flexibility due to the fact that we do not receive each site's recruitment numbers until the end of each day. These statistics have been reviewed and approved by our study statistician.

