#### 3.5. Statistical Analyses

**3.5.1.** Primary Analysis. Using SAS 9.4, primary analyses will be performed based on an intentto-treat basis. Two-sided significance levels of p<0.05 will be used for all analyses. Demographic (ethnicity, age, marital status) and other baseline variables (e.g., severity and chronicity) will be compared for potential differences between study groups using descriptive statistics (means, standard deviations, proportions) and the associated statistical tests (t-tests, chi-square tests). Those who drop out of the study will also be compared to those completing the study on baseline indices including maternal education and occupation. The primary outcome of noninferiority in EPDS scores will be compared between groups (telemedicine vs in-person, and specialist vs NSP) at 3-months using a t-test. The assessment period will be extended in the event that there is a hiatus to treatment due to significant perinatal-related life events (e.g., giving birth, obstetrical complications or COVID-19). One t-test will be run to assess this and compare modes (is telemedicine non-inferior to in-person). Another t-test will be run to assess this and compare agents (is non-specialist non-inferior to specialist). Each t-test will look at the confidence interval around the difference in EPDS scores (say between telemedicine and inperson), and see if the upper bound contains the 10% (provider) or 13% (modality) noninferiority margin (upper bound for the case in which we take the difference to be telemedicine minus in-person). We will conduct a sensitivity analysis to examine potential differences in baseline and outcome depressive symptoms and anxiety symptom scores to determine whether participants who were recruited and received treatment during the COVID-19 outbreak differed significantly from the larger sample.

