In addition, we will run a linear regression model with mode, agent and a mode by agent interaction term to assess whether an interaction between mode and agent exists. In the unlikely event that randomization was not able to reduce bias by balancing out confounders, we will assess for confounding. This will be carried out by assessing each potential confounder individually in relation to the key predictor (mode or agent) and seeing if the potential confounder impacts the parameter estimate of the key predictor using the 10% change in estimate approach. The potential confounder would also need to be significantly related to the EPDS score outcome. Should any confounders exist, they'll will be included in all of the previously mentioned analyses. Rules on the number of variables allowed in a multivariable model will be followed. The rule on number of variables in a linear regression is to take the total number of observations divided by 10. Given our trial sample size, we will not have any concerns with overfitting our linear model for our covariates of interest (education level, marital status, ethnicity, baseline severity and chronicity, timing of treatment, compliance, perceived support and medication).

Our study statistician and two independent methodological consultants have reviewed and approved this plan of analysis.

**3.5.2. Secondary Analysis.** In our secondary analysis, we are interested in: i) assessing the trend in EPDS scores over time (baseline, 3, 6- and 12-months post-randomization) between

groups (telemedicine vs in-person, and specialist vs NSP). This will involve the use of linear mixed models adjusting for possible covariates including baseline depression symptoms, medication, treatment dosage, and child age when assessing child outcomes. Mothers will be taken as a random effect and the models will include a treatment- by- time interaction term; ii) the same set of analyses will be conducted for anxiety symptoms (GAD-7). All child outcomes, including child mental development and the provision of psychosocial stimulation by the mother, will be compared between two groups (antenatal vs. postnatal) at 6-24 months post-childbirth using a two-sample two-sided t-test. Sensitivity analyses will be carried out excluding those who dropped out after first session to see if the results are comparable to the entire study group. No interim analyses will be carried out.

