1.6.1. Primary Aim 1 (Specialist vs. Non-Specialist) Comparison

The primary outcome measure is an EPDS mean score at 3 months post-randomization. The sample size calculation is based on an EPDS mean estimate of 7.93 (SD=4.68)³⁰. Using a non-inferiority margin of 10% (i.e., EPDS score of 0.79 in relation to the mean), and an alpha=0.05, we require 431 participants in each of the two groups (SP, NSP) to provide greater than 80% power ([Table 3](#)). To account for 10% drop out, the sample size is inflated to **N=958** (479 per group, SP vs. NSP). All sample size calculations were run using PASS Version 12³¹.

Table 3: Power Analysis of a Non-Inferiority Test of the Difference of Two Means

Power	N1/N2	Non-Inferiority Margin (NIM)	Actual Difference	Significance Level (Alpha)	Beta	Standard Deviation 1 (SD1)	Standard Deviation 2 (SD2)
0.80022	431/431	0.793	0.000	0.05000	0.19978	4.680	4.680

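### Protocol 3.5.2 uses baseline EPDS as both an outcome visit and a possible covariate in one mixed model, so the treatment-by-time test is an unadjusted change-score test, and any visit-specific standard errors reported from the model would be too small

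*Protocol*

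**What the plan says.** Protocol 3.5.2 (Secondary Analysis) gives its first aim as "assessing the trend in EPDS scores over time (baseline, 3, 6- and 12-months post-randomization) between" the arms, by delivery mode and by type of provider. The method named for this is "linear mixed models adjusting for possible covariates including baseline depression symptoms". A later sentence gives the structure: "Mothers will be taken as a random effect and the models will include a treatment- by- time interaction term".

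Protocol Table 6 measures depressive symptoms with the "Edinburgh Postnatal Depression Scale (EPDS") and lists the PHQ-9 separately, for response and remission. Baseline depression symptoms therefore means baseline EPDS. SAP Appendix 1 ticks the EPDS at screening and not in the baseline column, so there appears to be a single pre-treatment score to fill both roles.

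The SAP does not repeat the double use. Section 3.4.2.2 keeps baseline as an outcome visit with no baseline covariate, but its models name only antenatal versus postnatal. Section 3.4.2.3 models the delivery modes over time for severity moderation and lists no baseline covariate. Neither section withdraws the Protocol model for the randomised groups.

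**The concern.** A woman's baseline score can inform a longitudinal model as a response or as a covariate. In a random-intercept model it cannot properly do both.

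- **Treatment-by-time.** A covariate that is constant within a woman, with one slope for all visits, drops out of every between-visit contrast. The stated adjustment then does nothing for the only test the section names.
- **Arm difference at one visit.** The model forces one slope on all four visits. At baseline the true slope is 1, because the score is regressed on itself; at follow-up it is smaller whenever correlation times SD ratio is below 1. The leftover baseline residual is artificially small and pulls down the pooled variance that the model applies to 3, 6 and 12 months.

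At stake are precision in the main overall comparison of the randomised groups on EPDS through 12 months, and honest intervals if visit-specific differences are reported from it. Protocol 3.5.3.1 and SAP 3.4.2.3 also follow the arms over time, but for severity moderation.

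**Working it through.** The documents give no power, sample size or standard error for this model, so there is no stated figure to reproduce for it. The borrowed inputs can be checked.

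**Inputs from the documents**
- Follow-up SD: "The sample size calculation is based on an EPDS mean estimate of 7.93 (SD=4.68"), SAP 1.6.1.
- Group size, for illustration: "431 participants in each of the two groups to provide greater than 80% power", Protocol 2.6. Check: 2 × [4.68 × (1.645 + 0.842) / 0.793]² = 430.7, which rounds up to 431. The ratios below do not depend on n.
- Test level: "Two-sided significance levels of p<0.05 will be used for all analyses", Protocol 3.5.1.

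**Assumptions not in the documents**
- Baseline SD s0 of 3.3 to 4.68 (entry is cut at EPDS 10 or more, so it may be below 4.68).
- Baseline to follow-up correlation r of 0.3 to 0.5, the same at each visit.
- Random intercept only, categorical time, complete data. Follow-up SD s1 = 4.68.

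**1. Treatment-by-time.** The covariate term is b·Y0 at every visit, so it cancels from (Yt − Y0). The contrast is the raw difference in mean change.
- Variance per woman for change: s1² + s0² − 2·r·s0·s1.
- Variance per woman with baseline as covariate only: s1²(1 − r²).

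| s0 | r | change | covariate only | ratio |
|---|---|---|---|---|
| 4.68 | 0.3 | 30.66 | 19.93 | 1.54 |
| 4.68 | 0.5 | 21.90 | 16.43 | 1.33 |
| 3.3 | 0.3 | 23.53 | 19.93 | 1.18 |
| 3.3 | 0.5 | 17.35 | 16.43 | 1.06 |
| 3.5 | 0.7 | 11.22 | 11.17 | 1.00 |

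The last row lies outside the assumed range and shows the loss vanishing. At 431 per group, s0 = 4.68 and r = 0.5, the standard errors are √(2/431 × 21.90) = 0.319 and √(2/431 × 16.43) = 0.276. In simulation (400 trials per setting) the interaction estimates with and without the covariate agreed to about 2e-12 and the standard error was unchanged. Type I error was 0.028 to 0.070, roughly nominal. With 20% dropout the equality is approximate, with differences up to about 0.1 point.

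**2. Visit-specific difference.** With balanced data the common slope is b = (1 + 3·r·s1/s0)/4. The residual variances are:
- baseline: R0 = (1 − b)²·s0²
- each follow-up visit: Rt = s1² + b²·s0² − 2·b·r·s0·s1

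The model's total variance is the average, (R0 + 3·Rt)/4, while the true variance at a follow-up visit is Rt. So model SE / true SE = √[(R0 + 3·Rt)/(4·Rt)], and two-sided error is 2·[1 − Φ(1.96 × ratio)].

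| s0 | r | b | R0 | Rt | average | SE ratio | two-sided error |
|---|---|---|---|---|---|---|---|
| 4.68 | 0.3 | 0.475 | 6.04 | 20.60 | 16.96 | 0.907 | 7.5% |
| 4.68 | 0.5 | 0.625 | 3.08 | 16.77 | 13.35 | 0.892 | 8.0% |
| 3.3 | 0.3 | 0.569 | 2.02 | 20.16 | 15.62 | 0.880 | 8.4% |
| 3.3 | 0.5 | 0.782 | 0.52 | 16.48 | 12.49 | 0.871 | 8.8% |

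Simulation agrees: at r = 0.5 with equal SDs, model SE 0.249 against an empirical 0.278 (formula: 0.249 and 0.279).

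**3. Share due to equal variances.** Without the covariate the pooled variance is (s0² + 3·s1²)/4. At s0 = 3.3 that is (10.89 + 65.71)/4 = 19.15 against 21.90, an SE ratio of 0.935 and an error of 6.7%. So 6.5 points of the 12 to 13% shortfall there, about half, would exist without the double use. At s0 = 4.68 none of it would.

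**4. Decaying correlation.** Over s0 of 3.0, 3.5 and 4.68 and r of 0.2 to 0.7, with correlation falling over time, the SE ratio was 0.79 to 0.99 and two-sided error 5.3 to 12.2%, worst at 12 months. The ratio stayed below 1 at every post-baseline visit.

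**5. Unstructured covariance with both roles kept.** As the slope approaches 1 the baseline residual vanishes and the likelihood has no maximum: the profile log-likelihood was −4561 at slope 0, −592 at 0.99 and +3378 at 0.9999 (n = 862). A richer covariance alone does not repair the model.

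**The case against.** Several points on the other side stand.

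- **Non-inferiority.** A reader might infer that the narrow intervals favour declaring non-inferiority. The documents do not support that. The non-inferiority tests for EPDS (Protocol 3.5.1, SAP 3.4.1) and GAD-7 (SAP 3.4.2.1) are 3-month t-tests. Protocol 3.5.2 speaks of a trend and an interaction, and sets no margin or visit-specific interval.
- **Validity.** The one named test keeps about nominal type I error. A comparison of change between randomised groups is legitimate; it is merely less efficient.
- **Uniqueness.** It would be wrong to call this the only analysis of the arms through 12 months, given Protocol 3.5.3.1 and SAP 3.4.2.3.
- **Attribution.** Not all of the standard-error shortfall comes from the double use (step 3).
- **GAD-7.** The named covariate is baseline depression, which is not the response in a GAD-7 model. The problem arises there only if baseline GAD-7 is the covariate.
- **Loose wording.** Covariates are called possible, and the form of time and the residual covariance are not given. The random effect for mother is read here as a random intercept.

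Two defences do not hold. The covariate list cannot belong only to child outcomes, because the same section analyses those by t-test; the phrase about child outcomes most naturally qualifies child age alone. And the SAP's silence is not a correction, since it supplies no overall trajectory model for the randomised groups in place of the Protocol's.

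**Conclusion.** The point holds for a secondary analysis. As written, the Protocol 3.5.2 EPDS model offers an adjustment that, with complete data, has no effect on its treatment-by-time test. The cost is efficiency: a variance 1.06 to 1.54 times that of baseline-as-covariate for baseline SD 3.3 to 4.68 and correlation 0.3 to 0.5, falling to about 1.0 at higher correlation with a smaller baseline SD.

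If visit-specific differences are reported from a random-intercept fit, their standard errors are too small by about 9 to 13% under constant correlation (two-sided error 7.5 to 8.8%), and by 1 to 21% over the wider range tried under decaying correlation. Part of this reflects unequal variances when the baseline SD is below 4.68. The direction did not change over the settings examined; the size rests on correlations and a baseline SD that the documents do not state. The primary conclusions are untouched.

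**What to change.** Use baseline once in Protocol 3.5.2, in one of two forms:

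1. Responses at 3, 6 and 12 months only, with categorical visit, treatment-by-visit, baseline-by-visit and an unstructured covariance; or
2. Baseline kept as a response with a mean common to the arms, an unstructured covariance, and no baseline covariate.

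Say which baseline score enters the GAD-7 model. Add the two randomised comparisons to SAP 3.4.2.2 in the same form, since it now names only antenatal versus postnatal.

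In simulation the first form (fitted with baseline-by-visit terms) gave 3-month standard errors close to the empirical ones (ratio 0.97 to 1.08) and null rejection of 0.035 to 0.070. No new data are needed. The cost is a small change of text, which may need a formal amendment under Protocol 5.2.

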- **3.5.3. Subgroup Analyses.** Moderating effects will be conducted to determine whether delivery mode (telemedicine vs. in-person) or agent (specialist vs. non-specialist) have differential effects as a function of initial severity, whether mothers who receive antenatal treatment have lower depressive symptoms at 12-months post-enrollment than those who receive postnatal treatment; and whether children whose mothers receive the antenatal treatment have higher child development scores at 6-24 months post child birth than those children whose mothers receive postnatal treatment.
- **3.5.3.1.** Clinical Severity. Tests of moderation will be conducted to determine whether delivery mode (telemedicine vs. in-person) or agent (specialist vs. non-specialist) influence mothers who are severely depressed (EPDS>19). We expect 10 to 15% of our sample to be severely depressed (EPDS>19). A 2-group comparison with 75 per group and an assumed mean EPDS score of 20.0 (SD=7.0 , will provide 80% power, with an alpha of 0.05, to detect a mean change of 2.3 or greater. Our current sample size including those within severity subgroups described above will be adequately powered to detect medium effect size differences of HTE of symptom severity between groups. This indicates that we have adequate power for clinically meaningful tests. The two groups' (specialist vs non-specialist) EPDS scores at 3-months will be compared using a two-sided two-sample t-test. Change in EPDS score over time (baseline and every 3 months, post-randomization) will also be compared using linear mixed models. We will also examine this on anxiety symptoms at 3-months post randomization.

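### Protocol 3.5.3.1: 75 severe women per group at SD 7.0 can detect 3.2 EPDS points, not 2.3, and the mean and SD entered cannot describe their entry scores

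*Protocol*

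**What the plan says.** Protocol 3.5.3.1 (Clinical Severity) asks whether delivery mode or provider type may "influence mothers who are severely depressed (EPDS>19"). It gives the expected size of this group: "We expect 10 to 15% of our sample to be severely depressed (EPDS>19").

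The power statement has three parts. The size is "A 2-group comparison with 75 per group". The distribution is "an assumed mean EPDS score of 20.0 (SD=7.0"), cited to a paper on EPDS severity ranges. The result is that this "will provide 80% power, with an alpha of 0.05, to detect a mean change of 2.3 or greater". The section then concludes that power is adequate for clinically meaningful tests. For specialist versus non-specialist, "EPDS scores at 3-months will be compared using a two-sided two-sample t-test".

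Three other places bear on this:

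- Protocol 2.6, for 3-month EPDS in the whole trial: "The sample size calculation is based on an EPDS mean estimate of 7.93 (SD=4.68").
- SAP Appendix 2, which classes EPDS 20 to 30 as severe.
- SAP 3.4.2.3, the SAP's section on the same aim. It uses linear mixed models and states a requirement of 44 participants with a 10% non-inferiority margin. It does not repeat 75 per group, 20.0, 7.0 or 2.3.

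**The concern.** The statement contains everything needed to check it: two groups, 75 each, SD 7.0, two-sided 0.05, 80% power. Those inputs give a detectable difference well above 2.3.

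The mean and SD also look out of place. The subgroup is defined by an entry score of 20 or more, yet its assumed mean sits at the bottom of that range with a wide SD.

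At stake is how a null result in severe women is read. A reader who trusts the printed figure would take it as good evidence against a provider difference of 2.3 points, when the stated design would miss a true difference of that size about half the time.

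**Working it through.** **Inputs.** n = 75 per group, SD 7.0, difference 2.3, 80% power and alpha 0.05 from Protocol 3.5.3.1, with the two-sided two-sample t-test named there. The alternative SD of 4.68 and N = 1,230 come from Protocol 2.6. The severe range of 20 to 30 comes from SAP Appendix 2.

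**1. The printed figure.** Detectable difference = SD × (1.960 + 0.842) × √(2/n).

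- SD 7.0: 7.0 × 2.802 × √(2/75) = 3.20 (3.22 with the exact t-distribution). The printed 2.3 is not reproduced.
- Power at 2.3: the standard error is 7.0 × √(2/75) = 1.143, and 2.3/1.143 − 1.960 = 0.052, which gives 52% (51.6% with t).
- Group size for 80% power at 2.3: 2 × (7.0 × 2.802/2.3)² = 145.4, so 146 per group, or 147 with t.
- A one-sided 0.05 test does not rescue it: 2.84 points detectable, 64% power at 2.3.

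**2. What would give 2.3.** Three variants come close: a one-sample or paired test in 75 women at SD 7.0 (2.26; 2.29 with t), 150 per group at SD 7.0 (2.26), or 75 per group at SD 5.0 (2.29; 2.30 with t). None is the stated design, and the documents do not show which, if any, was used.

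**3. The plan's own 3-month SD.** 4.68 × 2.802 × √(2/75) = 2.14 (2.16 with t), and power at 2.3 is 85%.

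| SD | Detectable at 80% (t) | Power at 2.3 (t) |
|---|---|---|
| 7.0 | 3.22 | 52% |
| 5.0 | 2.30 | 80% |
| 4.68 | 2.16 | 85% |

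**4. Size of the subgroup.** 75 per group is 150/1,230 = 12.2% of the sample. The expected 10 to 15% of 1,230 is 62 to 92 per provider group, or 55 to 83 after 10% dropout. At SD 7.0, the sizes after dropout detect 3.73 to 3.04 points.

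**5. 20.0 (SD 7.0) as entry scores.** On the range 20 to 30 the largest possible SD is (30 − 20)/2 = 5.0. A mean of 20.0 is the lower limit, so every score would be 20 and the SD would be 0. The pair is impossible.

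**6. 20.0 (SD 7.0) as 3-month scores.** On the 0 to 30 scale a mean of 20.0 allows an SD up to √(20 × 10) = 14.1, so the pair is possible in itself, though it implies almost no improvement. Set it against an overall 7.93 (SD 4.68). With a share p severe, the other women must average (7.93 − 20p)/(1 − p). The overall variance is smallest if those women all score the same:

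p × (7.0² + 12.07²) + (1 − p) × (other mean − 7.93)²

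- p = 10%: 19.47 + 1.62 = 21.09, SD 4.59.
- p = 15%: 29.20 + 3.86 = 33.06, SD 5.75.

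The stated 4.68² = 21.90 is passed at p of about 10.4%. On this reading, the two sets of inputs cannot both hold over most of the plan's 10 to 15% range.

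**7. Which input causes that clash.** Keep SD 7.0 and lower only the severe women's 3-month mean. With 15% severe and mean 12, an overall 7.93 (SD 4.68) needs the others at mean 7.2, SD 3.7. With mean 14, they need SD 3.1. Both are attainable, so the clash comes from the mean of 20.0. The mean does not enter the formula in step 1.

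**The case against.** The strongest reply is that SD 7.0 is the cautious choice. A subgroup may vary more than the whole sample, and at the plan's 3-month SD of 4.68 the 2.3 is met with 85% power. That is correct, but the protocol prints 2.3 alongside SD 7.0, and that statement fails.

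A reader might go further and infer that the severe-subgroup inputs contradict the primary sample size, so that either SD 7.0 is wrong or 4.68 is too small and Aim 1 is underpowered. The documents do not support this. Section 3.5.3.1 never says that 20.0 is a 3-month mean, and the clash exists only on that reading. Even then it comes from the mean, and SD 7.0 fits an overall SD of 4.68 if severe women average 12 to 14 at 3 months. The two pairs are separate planning values cited to separate sources, so nothing here shows that 4.68 is too small.

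It can also be said that this is a secondary analysis, that recruitment was planned to end in March 2023, and that confidence intervals will show the precision achieved. All of that stands. It limits the weight of the point but does not make the printed figure correct.

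**Conclusion.** The power statement in Protocol 3.5.3.1 is wrong as written. At its own inputs the detectable difference is 3.2 points rather than 2.3, and power at 2.3 is about 52% rather than 80%. This rests only on the stated two-group, two-sided t-test with 75 analysed per group and SD 7.0.

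Separately, 20.0 (SD 7.0) cannot be the entry distribution of women scoring 20 to 30. As a 3-month distribution it is incompatible with 7.93 (SD 4.68) once more than about 10.4% of women are severe. This makes the pair unsuitable as printed and its time point and population unclear. It does not by itself show that SD 7.0 is wrong.

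The true 3-month SD in severe women is not given. Between the plan's two SDs, the detectable difference runs from about 2.2 to 3.2 points. The primary sample size is not affected.

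**What to change.** In Protocol 3.5.3.1:

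- Replace 2.3 with 3.2 points at SD 7.0, or keep 2.3 and state about 52% power. Show about 2.2 points at SD 4.68 as the alternative.
- Delete or correct the mean of 20.0, and state the time point and population of the SD used.
- Remove the sentence on adequate power, or qualify it with the detectable difference.

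Reconcile 75 per group with the 44 participants in SAP 3.4.2.3, so that both documents state one size, one set of inputs and one type of comparison for this aim.

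The cost is wording and a less favourable stated detectable difference. Recruitment, conduct and the primary analysis do not change.

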- **3.5.3.2. Perinatal Period.** This model will also test whether expectant mothers who receive antenatal treatment benefit more in terms of reduced depressive symptoms than mothers who receive postnatal treatment at 12-months post-randomization. A 2-group comparison with 200 per group and an assumed mean of EPDS score of 7.93 (SD=4.68) will provide 90% power, with an alpha of 0.05, to detect a mean change of 1.5 points. This allows us to detect a drop corresponding to a small effect size of 0.3 (i.e., a drop to mean 6.43 on the EPDS). The two groups' (antenatal vs. postnatal) EPDS scores at 3-months will be compared using a two-sided two-sample t-test. Change in EPDS scores over time (baseline and every 3 months, post-randomization) also will be compared using linear mixed models including the interaction between group and time. We will examine anxiety symptoms at 12-months post randomization in a linear mixed model controlling for relevant covariates including child age.

We will examine the hypothesis of whether the subset of mothers (up to 75% of the sample) who receive the antenatal treatment will benefit more in terms of improved child

outcomes at 6-24 months than mothers who receive postnatal treatment. A 2-group comparison of 238 per group (antenatal vs. postnatal) and an assumed mean on any Bayley IV raw subscale score of 100, SD=15 to assess child mental development will provide 80% power, with an alpha of 0.05 to detect a mean clinically-significant change of 3.0 units. Raw and standardized Bayley IV scores of the two groups' children (antenatal vs. postnatal) at 12 months will be compared using a two-sided, two-sample t-test.

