3.4.2.4. Analysis for Secondary Aim 3: Perinatal Period and Child Development

Another secondary aim is to explore whether the timing of the treatment (antenatal vs. postnatal) influences child mental development at 6 to 24 months post childbirth.

All child outcomes, including child mental development and the provision of psychosocial stimulation by the mother, will be compared between two groups (antenatal vs. postnatal) at 6-24 months post childbirth using a two-sample two-sided t-test. We will require a sample of 393 participants in each of the two groups to detect a mean clinically-significant change of 3.0 units with 80% power and an alpha of 0.05. Similar comparisons will be run between the primary comparison arms (SP vs NSP; in-person vs telemedicine). Sensitivity analyses will be carried out excluding those who dropped out prior and after first session to see if the results are comparable to the entire study group. We will adjust for time since treatment by including it as a variable in the regression model comparing antenatal vs. postnatal.

We will examine the hypothesis of whether the subset of mothers (up to 75% of the sample) who receive the antenatal treatment will benefit more in terms of improved child outcomes at 6-24 months than mothers who receive postnatal treatment. A 2-group comparison of 393 per group (antenatal vs. postnatal) and an assumed mean on any Bayley IV²⁷ raw subscale score of 100, SD=15 to assess child mental development will provide 80% power, with an alpha of 0.05 to detect a mean clinically-significant change of 3.0 units. Raw and standardized Bayley IV scores of

the two groups' children (antenatal vs. postnatal) at 12 months will be compared using a two-sided, two-sample t-test.

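### Two Protocol power statements do not follow from their own inputs: the severity comparison has 52% power, not 80%, for 2.3 EPDS points, and the Bayley comparison has 59%, not 80%, for 3.0 units

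*Protocol*

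**What the plan says.** **Severity, Protocol 3.5.3.1.** The paragraph expects severe depression (EPDS above 19) in a minority: "We expect 10 to 15% of our sample to be severely depressed". It then sizes a comparison: "A 2-group comparison with 75 per group and an assumed mean EPDS score of 20.0 (SD=7.0", which "will provide 80% power, with an alpha of 0.05, to detect a mean change of 2.3 or greater". The test is named: "specialist vs non-specialist) EPDS scores at 3-months will be compared using a two-sided two-sample t-test". From this, and from a sentence on detecting medium-sized heterogeneity of treatment effect (HTE) by symptom severity, it concludes: "This indicates that we have adequate power for clinically meaningful tests".

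**Child development, Protocol 3.5.3.2.** "A 2-group comparison of 238 per group (antenatal vs. postnatal"), with a Bayley mean of 100 and an SD of 15, "will provide 80% power, with an alpha of 0.05 to detect a mean clinically-significant change of 3.0 units". The test is again a two-sided two-sample t-test.

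**Child development, SAP 3.4.2.4.** For the same mean, SD, difference, alpha, power and test, the SAP has: "A 2-group comparison of 393 per group (antenatal vs. postnatal"). Both documents allow antenatal mothers to be up to 75% of the sample.

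**Severity, SAP 3.4.2.3.** The SAP drops the 75-per-group statement. It plans linear mixed models and asks for 44 participants, citing a 10% non-inferiority margin, 10% dropout, alpha 0.05 and a literature reference.

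**The concern.** Each Protocol statement fixes every input to a standard power calculation, so the stated 80% can be checked directly, and neither survives. In the severity paragraph the figure supports a claim of adequate power. At the stated 2.3 points the comparison is close to a coin toss, so a null result could be misread as evidence that provider type makes no difference in severe mothers. Whether the delivery strategies work differently for certain women is one of the trial's stated questions (Protocol 1.2).

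For the Bayley outcome, the two documents give different sizes for one test: 2 × 238 = 476 children against 2 × 393 = 786. A reader cannot tell which one the trial relied on.

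**Working it through.** Power is from the noncentral t, alpha 0.05, two-sided unless stated. The normal approximation, power ≈ Φ(δ/SE − 1.96) with SE = SD × √(1/n₁ + 1/n₂), is shown so that each line can be followed by hand.

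**1. Severity (75 per group, SD 7.0, δ = 2.3)**
- SE = 7.0 × √(2/75) = 1.143; δ/SE = 2.012; Φ(0.052) = 52.1%. Noncentral t: **51.6%**. One-sided: 64.0%.
- Difference detectable with 80% power: **3.22 points**, or 0.46 SD.
- Sample needed for 80% at 2.3 points: 147 per group, 294 in all; 294/1,230 = 24%, against an expected 10–15%.
- At the expected share, 123 to 185 women, or about 62 to 92 per group before dropout, power at 2.3 points is 44% to 60%.
- The printed 80% can be recovered only from a one-sample (or paired) test with n = 75, which gives 80.2%. That this is how it arose is an inference.

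**2. The HTE sentence (moderation)**

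Moderation is the agent-by-severity interaction, not the contrast within severe mothers. Assume 75 severe and 1,230/2 − 75 = 540 other mothers per provider group, SD 7.0 in the severe and s in the others:

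SE = √(2 × 7.0²/75 + 2 × s²/540)

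| s in other mothers | SE | Power at 2.3 | Power at 3.5 (0.5 SD) |
|---|---|---|---|
| 7.0 | 1.220 | 47% | 82% |
| 4.68 | 1.178 | 50% | 84% |

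The within-severe comparison has 86% power at 3.5 points. That figure answers a different question and should not be attached to the HTE sentence.

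**3. Bayley (SD 15, δ = 3.0)**
- SAP figure first: 393 per group, SE = 15 × √(2/393) = 1.070; δ/SE = 2.804; power **80.0%**. It reproduces.
- Protocol figure: 238 per group, SE = 15 × √(2/238) = 1.375; δ/SE = 2.182; Φ(0.222) = 58.8%. Noncentral t: **58.6%**. One-sided: 70.3%. One-sample: 86.7%. None is 80%.
- Difference detectable with 80% power at 238 per group: 3.86 units.
- At the 75% antenatal ceiling, 25% of 1,230 is about 308 postnatal mothers, fewer than 393 before any loss. Using all children:

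| Loss | Antenatal / postnatal | Power at 3.0 units |
|---|---|---|
| 0% | 922 / 308 | 86% |
| 10% | 830 / 277 | 82% |
| 20% | 738 / 246 | 77% |

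**4. Minor items in the SAP**
- The 44: no mean, SD or power is given, nor whether it is a total or per group. As a benchmark, a two-group non-inferiority t-test with a 10% margin, one-sided alpha 0.05, an assumed 80% power and 10% dropout gives totals of 340 (mean 20.0, SD 7.0), 774 (8.71, 4.61) and 958 (7.93, 4.68; the SAP's own figure). None is near 44.
- GAD-7 margin: 0.13 × 8.71 = 1.132, printed as 1.142.

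**The case against.** **Mean change might be meant within a group.** A one-sample calculation does return 80% for the severity figure. But the text specifies two groups, 75 in each and a two-sample test. The next Protocol section also uses mean change for a between-group difference: 200 per group for 1.5 points (SD 4.68) gives 89% as a two-group test, against a stated 90%. This reading does not rescue the statement.

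**The SAP has moved on.** This is true. It carries 393 rather than 238, omits the 75-per-group statement and plans mixed models for severity. That lowers the consequence, but Protocol V20 still prints both figures, and they are wrong as printed.

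**The Protocol's conclusion is tied to a medium effect.** This stands in part. Under the assumptions above, power at 0.5 SD is 86% within severe mothers and 82–84% for the interaction. A reader might infer that the severity analysis is hopeless or that the adequacy claim is false at every effect size; the numbers do not support that. The claim fails at the stated 2.3 points.

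**The 44 may be right.** A reader might infer from the 340 to 958 benchmark that it is an error. The documents do not show this. It rests on a cited source not available here, it is attached to a repeated-measures model, and its SD and power are unstated. What can be said is that its inputs and purpose are missing, and that a non-inferiority margin does not by itself size a test of moderation.

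**Conclusion.** Both Protocol power statements are wrong as written: 52% instead of 80% for severity, 59% instead of 80% for Bayley. These two results use only inputs printed in the Protocol and the test it names. The interaction figures further assume 1,230 mothers split equally by provider, 75 severe in each group, and an SD of 4.68 to 7.0 in the others. The figures at the antenatal ceiling assume that the antenatal share actually reaches 75% and that loss is equal in both groups.

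It would be a mistake to conclude that the trial itself is undersized. These are secondary and subgroup calculations, and none enters the primary sample size of 1,226 (1,230 planned). The GAD-7 slip is 0.01 point and did not drive the SAP's 460: the correct 1.132 gives 458, while 1.142 would give 452.

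**What to change.** - **Protocol 3.5.3.1:** change 2.3 to 3.2 points, or keep 2.3 and state 52% power. Label the figure as specialist versus non-specialist within severely depressed mothers only. Do not rest the HTE sentence on it: either size the agent-by-severity interaction with its assumptions stated, or remove the claim of adequate power for moderation at 2.3 points.
- **Protocol 3.5.3.2:** replace 238 with 393 to agree with SAP 3.4.2.4. State that 393 postnatal children would not be available at the 75% antenatal ceiling, and give the power from using all children there (86%, 82% and 77% with 0, 10 and 20% loss). The same caveat belongs in the SAP.
- **SAP 3.4.2.3:** give the mean, SD, power and purpose behind the 44, and say whether it is a total or per group.
- **SAP 3.4.2.1:** change 1.142 to 1.132.

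The cost is text only: no extra participants, data or analyses, apart from the optional interaction calculation. The stated power for the severity subgroup becomes less favourable.
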